**Intercurrent Events (ICEs) and Corresponding Strategies (Refer to Table 2):**

**Table 2: ICEs and Their Corresponding Strategies**

ICEs	Strategy for Addressing Intercurrent Events
1. Discontinuation of treatment due to lack of efficacy, or due to an AE of worsening of psoriasis. 2. Initiation of other medication or therapy that could improve psoriasis (see Appendix 6.7).	Composite Strategy: The occurrence of these ICEs is captured in the variable definition as patients with these ICEs are considered non-responders.
3. Discontinuation of treatment for other reasons than ICE 1	Treatment Policy: Strategy targeting the effect of treatment assignment, regardless of the occurrence of this ICE.

Note: For patients experiencing multiple ICEs, ICE 2 will override ICE 3 and the composite strategy will be applied.

**Population Level Summary:** Difference in proportions between JNJ-77242113 and placebo.

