### 4.2.3. Analysis Methods

#### 4.2.3.1. Main Analytical Approach

Analysis for the co-primary endpoints will be based on FAS, including data from all randomized participants. Participants will be analyzed based on their assigned intervention group, regardless of the actual intervention received.

According to the co-primary estimands 1a and 1b, participants with ICEs 1-2 before Week 16 will be considered as non-responders in co-primary endpoints at Week 16. For participants with ICE

3, observed data after this ICE will be utilized in the analysis. For participants experiencing multiple ICEs, an ICE2 will override an ICE 3. After accounting for the ICEs for the primary estimands, participants with missing value for the co-primary endpoints at Week 16 will be considered as non-responders.

In the primary analyses, the proportion of PASI 90 responders and IGA 0 or 1 responders at Week 16 will be summarized by treatment group. To address the primary objective, a 2-sided ( $\alpha=0.05$ ) CMH chi-square test stratified by age group (adults, adolescents), baseline weight category for adults ( $\leq 90$ kg in adults,  $>90$ kg in adults, adolescents), and geographic region (AMER, EU, APAC) will be used.

Difference in response rates between the JNJ-77242113 group and the placebo group at Week 16 and their corresponding 95% CIs (using Miettinen-Nurminen method [[REFERENCES](#)]) will be calculated adjusting for age group, baseline weight category for adults, and geographic region using Mantel-Haenszel (MH) weights.

The study will be considered positive if the JNJ-77242113 group is significantly different from the placebo group for both co-primary endpoints. Both co-primary endpoints will be tested at a 2-sided  $\alpha$  level of 0.05. If at least one of the comparisons is not significant at the 2-sided  $\alpha$  level of 0.05, the co-primary endpoints will be considered not significant.

In addition, the proportion of PASI 90 responders and IGA 0 or 1 responders at Week 16 will be summarized by region, country, and investigator site. The coprimary endpoints will also be summarized and compared between treatment group among adolescent participants. To evaluate the consistency of the efficacy, subgroup analyses of the co-primary endpoints based on demographics, baseline disease characteristics and previous psoriasis medications and therapies will be performed. The detailed subgroup analyses for the coprimary endpoints are specified in Section 4.6.6.

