##### **4.2.3.2.1. Sensitivity Analysis 1**

Under the co-primary estimands, a sensitivity analysis using multiple imputation will be performed for each co-primary endpoint. After accounting for the ICEs, missing data will be imputed using multiple imputations (MI) by fully conditional specification (FCS).

More specifically, the missing PASI 90 response and IGA 0 or 1 response will be imputed with FCS logistic regression including treatment group, baseline PASI score or IGA score, PASI 90 response or IGA 0 or 1 response status through Week 16, age group, baseline weight category for adults, and geographic region in the model with seed = 789 and 500 imputations.

A CMH test stratified by age group, baseline weight category for adults, and geographic region will be used to obtain the CMH statistic for each imputed dataset.

The general association test statistic from the CMH test for each imputed dataset will be transformed using the Wilson-Hilferty transformation ([Wilson and Hilferty, 1931](#)) to create a more normal distributed statistic:

$$Z = \frac{(CMH)^{(1/3)} - 7/9}{(2/9)^{(1/2)}}.$$

The resulting transformed values will be combined using SAS PROC MIANALYZE to obtain an overall p-value for the CMH test.

The common risk differences and 95% CIs in co-primary endpoints will be calculated using Mantel-Haenszel stratum weights and Sato variance estimator ([Sato, 1989](#)) adjusting for age group, baseline weight category for adults, and geographic region for each imputed dataset. The resulting values will be combined to obtain an overall risk difference and 95% CI.

#### 4.2.3.2.2. Sensitivity Analysis 2

Under the co-primary estimands, another sensitivity analysis will be performed using a tipping point analysis with Bernoulli draws to impute missing PASI 90 and IGA 0 or 1 response status at Week 16 after ICEs are accounted for. The tipping point analysis involves the following distinct steps:

1. Some p will be assumed for each treatment group's response rate, which could vary by treatment group, to impute the response status (Yes/No) for participants with a missing response based on a Bernoulli distribution. This will be repeated 200 times with seed = 20240719 to generate 200 multiple imputations.

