#### **4.4.2.4. Analyses From Week 64 Through Week 156**

The efficacy analyses from Week 64 through Week 156 will be performed for participants randomized to JNJ-77242113 at Week 0, or participants randomized to placebo at Week 0 and crossed over to receive JNJ-77242113 at or after Week 16 based on following data handling rules for ICE and missing data.

- Modified Non-Responder Imputation (mNRI) for binary endpoints: participants with ICE 1 will be considered as non-responders from that point forward. After accounting for ICE 1, missing data will be imputed using the same multiple imputations (MI) method specified in Section 4.2.3.2.1 for sensitivity analysis 1.
- Observed Cases (OC) for binary endpoints: selected endpoints (e.g., PASI responses, and IGA responses) will be summarized based on the observed data. No ICE rules will be applied, and missing data will not be imputed.
- MMRM model for continuous endpoints: participants with ICE 1 will be considered as zero change or zero percent change from baseline from that point forward. Missing data will be accounted for through correlation of repeated measures in the MMRM model.

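### The multiple-imputation sensitivity analysis uses earlier response only as yes/no status and discards observed PASI depth, so its estimate may be modestly too high if poorer responders leave for reasons not coded as ICE 1 or 2

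*SAP*

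**What the plan says.** SAP 4.2.3.2.1 (Sensitivity Analysis 1) applies the ICE rules first and then imputes what is still missing. It specifies that "the missing PASI 90 response and IGA 0 or 1 response will be imputed with FCS logistic regression including treatment group, baseline PASI score or" the baseline value of IGA. The post-baseline and stratum terms follow: "PASI 90 response or IGA 0 or 1 response status through Week 16, age group, baseline weight category for adults, and geographic region". There are 500 imputations, with seed 789.

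Three other parts of the plan bear on this:

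- **ICE handling.** Under SAP 4.2.3.1, "participants with ICEs 1-2 before Week 16 will be considered as non-responders in co-primary endpoints at Week 16". SAP Table 2 defines ICE 1 as "Discontinuation of treatment due to lack of efficacy, or due to an AE of worsening of psoriasis"; ICE 2 is the start of other therapy that could improve psoriasis. These participants are never imputed.
- **Primary analysis and tipping point.** In the primary analysis, "participants with missing value for the co-primary endpoints at Week 16 will be considered as non-responders" (non-responder imputation, NRI). Sensitivity Analysis 2 is a two-arm tipping point that includes cases where missing JNJ-77242113 participants do worse than missing placebo participants.
- **Long-term analysis.** For Weeks 64 to 156, SAP 4.4.2.4 sets ICE 1 to non-response, after which "missing data will be imputed using the same multiple imputations (MI) method specified in Section 4.2.3.2.1" (the mNRI analysis).

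The Schedule of Activities (Protocol 1.3.1) has PASI and IGA scored at Weeks 0, 2, 4, 8, 12 and 16. No dropout or missing-data rate is stated in either document.

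**The concern.** Take two JNJ-77242113 participants with the same covariates, both below PASI 90 at every visit. One is at 20% improvement at Week 12 and the other at 89%. The model gives both the same chance of a Week 16 response. If participants with poor PASI are likelier to leave, their data may be missing at random given the PASI score but not given the yes/no status, and the poorer ones are imputed too favourably.

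The SAP does not discard depth elsewhere. For continuous PASI it relies on a repeated-measures model (4.3.2.3), under which missingness may depend on the observed scores.

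At stake are the accuracy of one sensitivity estimate and of the long-term response rates. At Week 16 the tipping point covers the same question. For Weeks 64 to 156 no tipping point or full non-responder analysis is planned, and the cited model names response status only through Week 16, with no stated adaptation to later visits.

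**Working it through.** **1. The plan's own figure.** The plan gives no figure for imputation bias, so its power statement is the reference. For PASI 90, with 59% of 400 against 5% of 200 and 2-sided 0.05 (SAP 5):

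- Pooled rate = (236 + 10)/600 = 0.41.
- Null SE = √(0.41 × 0.59 × (1/200 + 1/400)) = 0.0426.
- Alternative SE = √(0.59 × 0.41/400 + 0.05 × 0.95/200) = 0.0290.
- Power = Φ((0.54 − 1.96 × 0.0426)/0.0290) = Φ(15.7), above 99.9%, as SAP Table 9 states.

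**2. Bias simulation.** Log PASI ratios at Weeks 4, 8, 12 and 16 were simulated for 200,000 JNJ-77242113 and 100,000 placebo participants, calibrated to 59% and 5% at Week 16. Missing Week 16 status was filled in two ways: by sequential logistic imputation on treatment and earlier yes/no status, and by imputing the continuous score and then dichotomising. Baseline PASI, age, weight and region were left out of both models. IGA was not simulated.

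Assumptions not in the documents:

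- nominal dropout of 3 to 20%, equal in both arms;
- visit correlation of 0.8 to 0.9;
- SD of the log ratio 1.2 (JNJ-77242113) and 0.8 (placebo);
- PASI 90 at Weeks 4/8/12 of 5/25/45% and 0.5/2/3.5%;
- log-risk slope of dropout of 0.7 to 1.2 per SD toward worse PASI, or none, or 0.7 toward better PASI.

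Bias in the risk difference with yes/no history, in percentage points (true value about 54):

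| Nominal dropout | Worse PASI leaves, no ICE step | Slope 1.2, correlation 0.9, worst 40% of dropouts set to ICE 1 |
|---|---|---|
| 3% | +0.3 to +0.6 | not run |
| 5% | +0.4 to +1.1 | +0.3 |
| 10% | +0.9 to +2.1 | +0.5 |
| 20% | +1.8 to +4.1 | +1.1 |

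With dropout unrelated to PASI, the bias was −0.1 to 0.0. With better-PASI participants leaving, it was −0.1 to −0.9. Imputing continuous PASI was within 0.1 point of the truth in every scenario.

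**3. Where the 5% row comes from.** Bias in the JNJ-77242113 arm = share missing × (imputed − true response among the missing).

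- Mildest case: 0.049 × (52.3 − 41.5) = 0.53 points.
- Steepest case: 0.049 × (48.5 − 23.2) = 1.24 points.

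The smaller upward bias in the placebo arm brings the net bias in the difference to 0.43 and 1.08.

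**4. Effect of the ICE step.** The bias with the ICE step, relative to the same scenario without it, is 0.28/1.08 = 0.26 at 5%, 0.51/2.08 = 0.25 at 10% and 1.08/4.11 = 0.26 at 20%. About a quarter remains.

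**5. A second simulation.** It used 150 replicates per scenario, 400 against 200, correlation 0.85, dropout after Week 12 depending on Week 12 improvement, and no ICE step. It gave +0.5 to +0.9 points at 5% missing, +1.8 at 10% and +1.3 to +3.2 at 20%. This is the same direction and order of size.

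**6. Extreme bound on the main conclusion.** Take 20% missing per arm, with all missing JNJ-77242113 participants as failures and all missing placebo participants as responders. The rates are 0.59 × 0.8 = 47.2% and 0.05 × 0.8 + 0.20 = 24.0%. The pooled rate is (188.8 + 48)/600 = 0.395, and the SEs are 0.0423 and 0.0392. Power = Φ((0.232 − 1.96 × 0.0423)/0.0392) = Φ(3.80), still above 99.9%.

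**The case against.** The strongest reply is that the plan already removes most of the problem. Participants who stop for lack of efficacy or worsening psoriasis, or who start other psoriasis therapy, are non-responders before any imputation. Those who stop for other reasons but stay in the study keep attending (Protocol 7.1), and their observed data are used. Only the remainder is imputed, in a model that also contains treatment, baseline score, age group, weight category and region. This stands, and it is why the figures without an ICE step are too large for the planned procedure. It does not remove the point: a poor responder recorded as withdrawn consent or lost to follow-up (Protocol 7.2) is not ICE 1 and can reach the model.

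A reader might infer that the treatment effect is overstated outright. The documents do not support that. They give no dropout rate or mechanism, and the sign depends on who leaves.

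A reader might also infer that the dropout pattern of interest goes unexamined. It does not: the tipping-point grid, for example 0 to 100% in each arm independently, covers the response rates at issue.

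Sparse early PASI 90 counts might suggest separation in the logistic model. The documents give no early-visit rates, and separation was not shown.

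Finally, the risk-difference figures do not transfer to Weeks 64 to 156, where all participants are assigned active drug and there is no placebo contrast. There the issue is response rates that may be somewhat too high, by an amount not estimated here.

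**Conclusion.** The point holds in a conditional form. The imputation model discards PASI depth that the trial collects. If poorer responders leave for reasons not coded as ICE 1 or 2, the multiple-imputation estimate of the PASI 90 difference may be modestly too high. At 5% missing this is about 0.4 to 1.1 points of 54 before ICE handling. It is about 0.3 in the one steep scenario where an assumed 40% of dropouts are coded as ICE 1. All sizes rest on assumed dropout and trajectories and should be read as a range. For IGA 0/1 the mechanism is the same, but no size is available.

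The primary conclusion is not in question. Neither the NRI analysis nor the tipping point uses this model. NRI lay below the truth in every scenario: at 5% missing it gave 50.6 to 53.0 against about 54. The case for changing the text is that the correction is cheap, and that the long-term analysis lacks the backup available at Week 16.

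**What to change.** In SAP 4.2.3.2.1, add post-baseline PASI total scores from earlier visits as predictors in the FCS model for PASI 90, and earlier IGA scores for the IGA endpoint. Alternatively, impute PASI by predictive mean matching and then derive PASI 90. In either case, keep participants with ICE 1 or 2 as non-responders, and keep scores recorded after ICE 2 out of the imputation model so that the effect of other therapy does not inform the imputed values.

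Make the same change in 4.4.2.4, and state there that the predictors are scores from visits up to the one being imputed.

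The cost is SAP wording, a little more programming and a slightly larger imputation model. No new data are needed.

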#### 4.2.3.3. Supplementary Analyses

##### 4.2.3.3.1. Supplementary Analysis Sup1a and Sup1b (Treatment Policy Estimand)

The co-primary endpoints will also be analyzed utilizing the treatment policy estimand. For participants who experience an ICE through Week 16, the analysis will be performed using observed data regardless of intercurrent events. Participants with missing data will be imputed as non-responders. The same CMH test as for the primary estimand will be used.

#### **4.2.3.4. Per Protocol Analysis**

The co-primary efficacy endpoints will be evaluated for comparisons between JNJ-77242113 group and placebo group in the per protocol population based on the primary estimand. The same data handling rules and analysis method specified in Section 4.2.3.1 will be applied.

### **4.3. Secondary Endpoints Analysis**

#### **4.3.1. Key Secondary Endpoints/Estimands**

##### **4.3.1.1. Definition of Endpoints**

##### **4.3.1.1.1. Investigator's Global Assessment (IGA)**

Refer to section 4.2.1.2 for details.

Meeting the IGA 0 criteria: defined as having an IGA score of cleared (0).

##### **4.3.1.1.2. Psoriasis Area and Severity Index (PASI)**

Refer to section 4.2.1.1 for details.

Meeting PASI 75 criteria: defined as having  $\geq 75\%$  improvement in PASI from baseline.

Meeting PASI 100 criteria: defined as having 100% improvement in PASI from baseline.

The time to loss of PASI 75 response through Week 52: PASI 75 response will be assessed at each visit between Week 24 and Week 52. Participants who experience a loss of PASI 75 response ( $< 75\%$  improvement from baseline) at any visit between Week 24 and Week 52 will be considered as having an 'event'. The time to loss of PASI 75 response is defined as the time from rerandomization at Week 24 to the visit of loss of PASI 75 response. Participants who do not experience any event between Week 24 and Week 52 will be censored at the last disease assessment visit or Week 52.

The time to loss of PASI 90 response through Week 52: similar to the definition of time to loss of PASI 75 response except using loss of PASI 90 response, which is when  $< 90\%$  improvement from baseline is observed.

##### **4.3.1.1.3. Psoriasis Symptom and Sign Diary (PSSD)**

The PSSD will be utilized in the adult and adolescent population and includes PRO questionnaires designed to measure the severity of psoriasis symptoms and signs for the assessment of treatment benefit. There are two versions of the PSSD: a 24-hour recall version that asks the participant to answer the questions thinking about the last 24 hours through Week 16 visit and a 7-day recall version asking the participant to answer the questions thinking about the last 7 days after Week 16. Both versions of the PSSD are self-administered PRO instruments and include 11 items in total, with 5 items covering symptoms (itch, pain, stinging, burning and skin tightness) and 6 items covering participant-observable signs (skin dryness, cracking, scaling, shedding or flaking, redness and bleeding). A 0 to 10 numerical rating scales for severity is used for each item. For both the 24-

hour and 7-day recall versions, two subscores will be derived each ranging from 0 to 100: the PSSD symptom score and the PSSD sign score. For all scores, a higher score indicates more severe disease.

The calculations of PSSD symptom, sign scores, and item score are listed below:

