Randomization		X							X							Randomization at W24 is rerandomization for adult participants receiving JNJ-77242113 from W0 to W24.
Dispense study intervention		X	X	X	X	X	X	X	X	X	X	X	X	X		Dispense study intervention after all other procedures. Study intervention may also be dispensed between visits.
Administer study intervention		Oral study intervention will be self-administered daily (Section 6.1).														Study intervention will be taken at the site during the baseline (W0), W4, and W16 visits, where both a pre- and post-dose PK sample will be drawn. At W16 study intervention will be

Period	Screening	Placebo-controlled					JNJ-77242113 Treatment		Randomized withdrawal and retreatment						Unscheduled ^{a,b}	Notes: See Section 1.3.2 for Early Termination Visit procedures.
Week (W)	-5-0	0	2	4	8	12	16	20	24	28	32	36	44	52		
Visit Window (days)			±2	±2	±4	±4	±4	±4	±4	±4	±4	±4	±4	±4		
Study Procedure																
																taken from a newly dispensed drug blister pack at the visit.
Study intervention accountability			X	X	X	X	X	X	X	X	X	X	X	X	X	
Efficacy Assessments																
PROs: Complete in the order shown before any tests, procedures, or consultations for all visits unless otherwise noted.																
PSSD (24-hour recall)	Daily Diary beginning at Screening through W16.															
PSSD (7-day recall)							X	X	X	X	X	X	X	X	X	
DLQI or CDLQI		X	X	X	X	X	X	X	X	X	X	X	X	X	X	
GenPs-SFQ		X			X		X		X			X		X		W8-W52: Collect only for participants with active genital psoriasis at W0. Only for participants ≥18 years of age.
PROMIS-29 or PROMIS-25		X			X		X		X			X		X		PROMIS-25 is only for participants <18 years of age.
TSQM-E							X							X		Effectiveness domain only (Section 8.2.10.7).
EQ-5D-5L		X			X		X		X			X		X		
PsA Pain Assessment		X			X		X							X		W8-W52: Collect only for participants with a diagnosis of PsA at or before screening.
PsA Disease Activity Assessment		X			X		X							X		
Acceptability and palatability assessment		X					X									Only for participants <18 years of age.
ClinROs																
IGA	X	X	X	X	X	X	X	X	X	X	X	X	X	X	X	
PASI	X	X	X	X	X	X	X	X	X	X	X	X	X	X	X	
BSA	X	X	X	X	X	X	X	X	X	X	X	X	X	X		

Period	Screening	Placebo-controlled					JNJ-77242113 Treatment		Randomized withdrawal and retreatment						Unscheduled ^{a,b}	Notes: See Section 1.3.2 for Early Termination Visit procedures.
Week (W)	-5-0	0	2	4	8	12	16	20	24	28	32	36	44	52		
Visit Window (days)			±2	±2	±4	±4	±4	±4	±4	±4	±4	±4	±4	±4		

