**PSSD Item Score (0-10)**

- a. PSSD 24-hr recall, each individual item score over seven days is averaged into a weekly item score (i.e. 7 days [from day -7 to -1] prior to a visit).
- b. PSSD 7-day recall, each individual item response is used as the score.

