#### **4.4.2.13. Analyses Related to Psoriasis Symptom and Sign Diary Through Week 24**

- The change from baseline in PSSD symptom score and sign score will be summarized over time through Week 24 by treatment group.
- The proportions of participants who achieve a PSSD symptom score of 0 and sign score of 0 will be summarized over time through Week 24 among participants with a baseline PSSD symptom score  $>0$ , and baseline sign score  $>0$  respectively by treatment group. Additionally, these endpoints will be summarized over time by treatment group and age group.
- The proportion of participants who achieve a  $\geq 4$ -point improvement from baseline in PSSD itch score will be summarized over time through Week 24 among participants with baseline PSSD itch score  $\geq 4$ . Additionally, this endpoint will be summarized over time by treatment group and age group.
- The change from baseline in each PSSD individual scale score will be compared between treatment groups at Week 16.

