#### **From Week 64 Through Week 156**

- The change from baseline in PSSD symptom score and sign score will be summarized over time.
- The proportion of participants who achieve a PSSD symptom score of 0, sign score of 0, and  $\geq 4$ -point improvement from baseline in PSSD itch score will be summarized over time among participants with a baseline PSSD symptom score  $>0$ , and baseline sign score  $>0$ , and baseline PSSD itch score  $\geq 4$  respectively.

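### The exploratory PSSD over-time summaries cross a change of recall version at Week 16 without a break or bridge, so a step between Week 16 and Weeks 20–24 can come from the instrument

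*SAP*

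**What the plan says.** SAP 4.3.1.1.3 describes two versions of the diary. One is "a 24-hour recall version that asks the participant to answer the questions thinking about the last 24 hours through Week 16 visit". The other is "a 7-day recall version asking the participant to answer the questions thinking about the last 7 days after Week 16".

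They are scored differently. For the 24-hour version, "each individual item score over seven days is averaged into a weekly item score", using the seven days before the visit. At least four diary days are needed, with a 10-day look-back at baseline and Weeks 4, 8 and 16. For the other version the SAP says: "PSSD 7-day recall, each individual item response is used as the score". For both, the symptom score is ten times the mean of the symptom items, provided at least three of the five are available. The criteria for score of 0 and for itch response carry no reference to the recall version.

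SAP 4.4.2.13 then plans, for all participants: "The change from baseline in PSSD symptom score and sign score will be summarized over time through Week 24 by treatment group". The score-of-0 rates and the itch response follow the same pattern. Adolescents have a parallel set through Week 52. A separate block for Weeks 64 to 156 begins: "The change from baseline in PSSD symptom score and sign score will be summarized over time".

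In the protocol's Schedule of Activities (1.3.1), the 24-hour row reads "Daily Diary beginning at Screening through W16". The 7-day row carries nine marks. By column position these are Weeks 16, 20, 24, 28, 32, 36, 44 and 52 and the unscheduled visit. Neither document gives a bridging analysis, a statement of equivalence, a break in the display or a caveat.

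**The concern.** Within the Week 24 summaries (and the adolescent Week 52 summaries), points up to Week 16 come from one instrument and points from Week 20 onward from another, while the response rule stays the same. A reader of the table or plot would take any step after Week 16 as a change in symptoms.

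The timing makes this worse. The placebo arm crosses over to JNJ-77242113 at Week 16, and SAP 4.4.2.1 limits that group at Weeks 20 and 24 to participants who crossed over. A step in that arm therefore mixes drug effect, change of instrument and change of denominator. In the JNJ-77242113 arm treatment does not change between Weeks 16 and 24, so an instrument step could be read as growing or waning benefit.

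**Working it through.** The plan states no figure to reproduce. The check applies the SAP scoring rules to identical symptoms under both versions.

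**Inputs from the documents.** Five symptom items; score = 10 × mean of the item scores; diary item score = mean over 4 to 7 recorded days; 7-day item score = one response; response = score exactly 0; missing = non-responder (SAP 4.3.1.3.1, carried over by 4.3.2.3 and 4.4.2).

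**Inputs assumed.** Whole-number ratings from 0 to 10, and how a participant condenses a week into one answer. The documents give neither the recall behaviour nor any data on it.

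**1. Number of zeros required.** A diary score of 0 needs a zero on every recorded day for every available item: from 4 × 3 = 12 up to 7 × 5 = 35 zeros. A 7-day score of 0 needs 3 to 5.

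**2. One mild day.** Suppose one item is rated 1 on one day and everything else is 0.
- Diary, 7 days: 10 × (1/7)/5 = 0.29, not a responder. With 4 recorded days including the bad one: 10 × (1/4)/5 = 0.50, not a responder.
- 7-day form answered as an average (0): score 0, a responder.
- 7-day form answered as the worst day (1): 10 × 1/5 = 2.0, not a responder, and the score is 1.71 points above the 7-day diary's 0.29.

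So averaging moves the score-of-0 rate, while worst-day recall can leave that rate alone and move the mean.

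**3. Closed form.** If each day is fully clear with probability p, independently, the diary rate is p to the power of the number of recorded days.
- p = 0.95: 69.8% (7 days), 81.5% (4 days), against 95% for one answer that reflects a single day.
- p = 0.90: 47.8%, 65.6%, against 90%.

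**4. Simulation.** 200,000 participants; each person's chance of a clear day is drawn from a Beta distribution with mean 0.5 and concentration 1; a non-clear day has one randomly chosen item rated 1. Percentage with score 0:
- diary, 7 days: 21.0%
- diary, 4 days: 27.4%
- 7-day form, rounded average: 95.2%
- 7-day form, last day: 49.9%
- 7-day form, worst day: 21.0%

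The step is therefore up (average or last day), nil (worst day, complete diary: 21.0% to 21.0%) or down (worst day, 4-day diary: 27.4% to about 21%). The same ordering appeared for means of 0.3, 0.5 and 0.7 with concentrations of 0.3, 1 and 3. The averaging figure is extreme because a bad day in this model never exceeds one item rated 1.

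**5. Itch response (at least 4 points).** Take a diary baseline of 51/7 = 7.29 and a later week with mean 24/7 = 3.43. Improvement on the diary is 3.86, which fails. A 7-day answer of 3 gives 7.29 − 3 = 4.29, which passes.

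**6. Missingness alone.** If 40% are truly at 0, and 10% of diary scores but 3% of 7-day scores are missing (both assumed), non-responder imputation gives 0.40 × 0.90 = 36.0% and 0.40 × 0.97 = 38.8%.

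**The case against.** The strongest reply is that little depends on these summaries. They are exploratory and carry no multiplicity control (SAP 2.1 and 4.4.2). Both arms use the same version at each visit. The only between-group PSSD comparison in 4.4.2.13 is at Week 16. After Week 16 there is no placebo control, so the step in the crossover arm was never a randomised comparison. All of this stands, and it makes the point an inexpensive improvement to reporting, with no bearing on the trial's conclusions.

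Two wider readings are tempting, and the documents do not support them.
- A reader might infer that one mixed series runs to Week 156, or that adult maintenance to Week 52 is distorted. Weeks 64 to 156 are a separate analysis with its own data rules (SAP 4.4.2.4), and every point in it is 7-day data. SAP 4.4.2.13 lists no adult PSSD summary for Weeks 24 to 52. What crosses the switch is Weeks 20 and 24 for everyone, plus the adolescent summary in about 60 participants. The later block shares only the 24-hour baseline, through change from baseline, itch response and the baseline filters.
- A reader might infer that the score-of-0 rate must rise, or that only that rate is at risk. Both depend on participants averaging their week. Under worst-day recall the rate can stay level or fall while the mean score rises.

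It can also be said that splitting the display does not solve everything. That is correct: no 7-day baseline is scheduled, so later change scores and itch response remain cross-version.

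**Conclusion.** The point holds for the Week 24 summaries in all participants and the Week 52 summaries in adolescents. Two differently scored versions are placed in one over-time summary under one response rule, and the change falls at the placebo crossover. A step after Week 16 cannot be attributed to symptoms on the plan as written.

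The size and direction are unknown. The figures above are illustrations under assumed recall behaviour and symptom patterns, not estimates for this trial.

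The co-primary endpoints do not use the PSSD. The key secondary PSSD endpoints (Weeks 4, 8 and 16) and the Week 16 other secondary PSSD endpoints use the 24-hour version for both baseline and outcome, so none of them is affected. The availability of bridging data rests on the column position of the Week 16 mark in the 7-day row of the Schedule of Activities.

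**What to change.** In SAP 4.4.2.13:

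1. Report Week 16 under both recall versions by arm, with their agreement on score of 0 and the mean difference in score.
2. Break the over-time displays at Week 16: the 24-hour version for Weeks 2 to 16, the 7-day version from Week 16 onward.
3. Base any within-arm statement about the period after Week 16 on the Week 16 7-day value.
4. Footnote that change from baseline and itch response after Week 16, including Weeks 64 to 156, still use a 24-hour baseline because no 7-day baseline is collected.

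The cost is a few lines of SAP text and one extra table. No new data are needed, given that both versions are scheduled at Week 16. The downside is that the PSSD results no longer form a single continuous curve from baseline.
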